## **7.3. Assessment of Allergic Sensitisation**

### **7.3.1. Skin Prick Testing**

At Screening, SPT (performed on the flexor aspect of the forearm) with birch pollen allergen will be performed at the clinical research unit. Positive and negative controls will be included in the assessment (histamine and diluent, respectively).

Prior to the SPT, drugs that might interfere with this assessment (particularly oral antihistaminics and local skin application of glucocorticoids) must be avoided for 5 days.

The response to SPT will be assessed by measuring the orthogonal diameter of the wheal, at the mid-point of the longest axis, and the average of the longest and the orthogonal diameter will be calculated. Pseudopodia will not be assessed.

The mean wheal diameter of the negative control must be < 2 mm for the test to be considered valid. If the negative control wheal diameter is  $\geq$  2 mm, the test should be repeated on another day. The positive control should give a reaction with a wheal diameter  $\geq$  3 mm greater than the negative control.

### **7.3.2. Allergen-Specific IgE**

A blood sample (10 ml) will be collected for the measurement of Bet v allergenic components (Bet v 1, Bet v 2, Bet v 4, Bet v 6)-specific IgE levels in serum by ImmunoCAP® at the Screening and other time points indicated in Tables 11-13 (see Section 6.5.).

In addition, the following allergen-specific IgE levels in serum will be measured at Screening only to allow better understanding of the allergic sensitization profile of the study participants:

- Alder, hazel, peanut, hazelnut, kiwi, celery, apple, peach, soy (cross-reactive allergens, Profilin 10 protein).
- Equine, cat, dog, mugwort, Timothy Grass, *Dermatophagoides pteronyssinus*, *Dermatophagoides farinae* and *Cladosporium herbarum*

#### **7.4. Assessment of Efficacy**

There are no efficacy assessments included in this study.

#### **7.5. Assessment of Exploratory Immunological Biomarkers**

Blood samples will be collected for potential analysis of immunological biomarkers that may be related to the effects of immunotherapy, including birch pollen-specific immunoglobulins (IgG sub-classes and IgA), blocking antibodies, B and T cell phenotyping, and cytokines. The samples will be analysed in a qualified laboratory. After completion of the analyses the remaining blood will be destroyed, unless the subject has given separate, optional consent for their further storage for additional potential biomarker analyses related to the purposes of the study.

#### **7.6. Assessment of Pharmacokinetics**

There are no pharmacokinetic assessments included in this study.

#### **7.7. Optional Sub-study: Assessments**

A separate optional sub-study may involve collection of medical history information and a blood sample collection for analysis of exploratory immunological biomarkers after the 2021 birch pollen allergy season, i.e. in the autumn of 2021. Only participants in cohorts 2 - 4 will be invited to take part in this sub-study. This sub-study does not involve any other assessments or procedures except an interview and the blood sample collection. Separate consent will be asked for participation in this optional sub-study.

## 8. ADVERSE EVENTS

The Investigator and his staff are responsible for detecting, documenting and reporting events that meet the definition of an AE. Adverse events will be reported, irrespective of whether they are volunteered, elicited, or noted on physical examination or medical review, throughout the study, from the signing of the ICF until the Follow-up visit.

AEs occurring prior to the first treatment administration, but after obtaining informed consent will be reported separately from TEAEs, which will be of particular interest.

Definitions of AEs and serious adverse events (SAE) and the documentation and reporting of them within this study will follow the GCP, EU and Finnish national guidance.

### 8.1. Definition of Adverse Events

An AE is any untoward medical occurrence experienced by a study subject, temporally associated with the use of a medicinal product, whether or not considered related to the medicinal product. For the current study, all AEs will be coded using the Medical Dictionary for Regulatory Activities (MedDRA, version 22.1) by 4Pharma in co-operation with CRST.

An AE can therefore be any unfavorable and unintended signs (including clinically relevant changes in laboratory parameters), symptoms, diseases (new or exacerbated) or accidents temporally associated with the use of a medicinal product.

AEs comprise all disturbances of general health status. Events meeting the definition of an AE include:

- Any abnormal laboratory test results (haematology, clinical chemistry, or urinalysis) or other safety assessments (e.g. ECG, spirometry, vital signs measurements), including those that worsen from baseline, and the Investigator considers them clinically significant.
- Exacerbation of a chronic or intermittent pre-existing condition, including either an increase in frequency and/or intensity of the condition.
- New conditions detected or diagnosed after study treatment administration even though it may have been present prior to the start of the study.
- Signs, symptoms, or the clinical sequelae of a suspected interaction with the study treatment.
- Signs, symptoms, or the clinical sequelae of a suspected overdose of either study treatment or a concomitant medication (overdose per se will not be reported as an AE/SAE unless this is an intentional overdose taken with possible suicidal/self-harming intent. This should be reported regardless of sequelae).

Events that do not meet the definition of an AE include:

- Any clinically significant abnormal laboratory findings or other abnormal safety assessments that are associated with the underlying disease, unless judged by the Investigator to be more severe than expected for the subject's condition.
- The disease/disorder being studied, or expected progression, signs, or symptoms of the disease/disorder being studied, unless more severe than expected for the subject's condition.
- Medical or surgical procedure (e.g., endoscopy, appendectomy); the condition that leads to the procedure is an AE.
- Situations where an untoward medical occurrence did not occur (social and/or convenience admission to a hospital).
- Anticipated day-to-day fluctuations of pre-existing disease(s) or condition(s) present or detected at the start of the study that do not worsen.

## **8.2. Definition of Serious Adverse Events**

A SAE is any AE occurring during the study that results in any of the following outcomes:

- Results in death
- Is life-threatening. The term 'life-threatening' in the definition of 'serious' refers to an event in which the subject was at risk of death at the time of the event. It does not refer to an event, which hypothetically might have caused death, if it were more severe.
- Requires hospitalization or prolongation of existing hospitalization. This is defined as the subject being hospitalised overnight. Any pre-planned or anticipated in-hospital visits must be documented in advance at the screening visit and will be excluded from this category.
- Results in significant disability/incapacity.
- Is a congenital anomaly/birth defect.
- Is an important medical event that may require medical or surgical intervention to prevent one of the above outcomes.

Medical and scientific judgement should be exercised in deciding whether expedited reporting is appropriate in other situations, such as important medical events that may not be immediately life-threatening or result in death or hospitalisation but may jeopardise the subject and may require intervention to prevent one of the other outcomes listed in the definition above. These should also be considered to be SAEs.

## **8.3. Definition of Suspected Unexpected Serious Adverse Reactions**

An unexpected adverse drug reaction is any adverse drug reaction (ADR), the specificity or severity of which is not consistent with the current IB of DM-101. In this FiH study, all adverse reactions to DM-101 will be considered unexpected. Suspected unexpected serious ADRs (SUSARs) are subject to expedited reporting to the CA by the pharmacovigilance provider (PV) of the study. The investigator reports all authority-reportable AEs to the Sponsor and the

pharmacovigilance provider, for reporting to the CA according to applicable legislation, and as agreed between the parties

#### **8.4. Definition of Adverse Events of Special Interest**

##### **8.4.1. Systemic Allergic Reactions**

All allergic reactions that occur after the initiation of IMP dosing should be recorded in the subject's medical records and also as an AE in the eCRF. If a systemic allergic reaction meets the definition of serious, then it should be classified as a SAE and will be recorded and reported in the same way as any other SAE.

[figure not shown]
In addition, all systemic allergic reactions must be graded, as defined by the WAO Subcutaneous Immunotherapy Systemic Reaction Grading System (Appendix 1) and be considered AEs of Special Interest (AESI). All Grade 2 to 5 systemic allergic reactions must be reported in an expedited manner to the Sponsor within 24 h from their occurrence.

##### Treatment of systemic allergic reactions

Systemic allergic reactions may be life-threatening and any suspected severe allergic reaction must be treated immediately.

All medications and medical equipment for the treatment of suspected, severe allergic (anaphylactic) reactions must be immediately available at the clinical research unit.

Figure 2 presents an example of an algorithm for the management of suspected anaphylactic reactions, proposed by the European Academy of Allergy and Clinical Immunology (EAACI). The Investigator will follow CRST's Standard Operating Procedure (SOP) for treating suspected anaphylactic reactions, and a copy of the Guideline and the SOP must be placed in the ISF. The subjects of cohorts 3 and 4 will be equipped with i.v. cannula until at least 4 h after the last injection of the day, and the i.v. route will therefore be available for fluid therapy and for administration of antihistaminics and glucocorticoids.

From Anaphylaxis: Guidelines from the European Academy of Allergy and Clinical Immunology Muraro A et al., 2014 Allergy. 69:1026-1045.

**Figure 2 Schematic illustration of the initial management of anaphylaxis proposed by the EAACI.**

If a delayed, systemic allergic reaction occurs following dosing, once a subject has left the clinical research unit, the subject should follow the action plan provided to him/her by the Investigator at Visit 2 (See Appendix 2). Subjects should also contact their health care provider or seek emergency medical attention, as indicated.

Subjects who develop Grade 3 and 4 systemic allergic reactions should be hospitalised overnight or monitored for at least 12 hours.

#### 8.4.2. Injection Site Reactions

All allergic reactions that occur after the initiation of IMP dosing should be recorded in the subject's medical records and also as AESI in the eCRF.

All Injection site reactions should be evaluated as AEs and also be graded on a five-point (0 to 4) scale for each of the following parameters: pain, tenderness, erythema/redness, induration/swelling (Table 14).

## 8.5. Recording of Adverse Events

When an AE or SAE occurs, it is the responsibility of the Investigator to review all documentation (e.g., hospital progress notes, laboratory, and diagnostics reports) relative to the event. The Investigator will then record all relevant information regarding the event in the subject's medical record and transcribe it to the eCRF.

When recording an AE / SAE, the following details must be given:

- Event observed (brief description using medical terminology)
- Start and stop dates and times
- Severity (Section 8.5.1.)
- Causality (Section 8.5.2.)
- Relationship to other events (e.g. study procedure or concomitant medication)
- Action taken (brief description)
- Outcome
- Serious (Yes/No)

When an AE occurs, the Investigator will attempt to establish a diagnosis of the event based on signs, symptoms, and other clinical information. In such cases, the diagnosis will be documented as the AE/SAE and not the individual signs/symptoms.

All AEs will be recorded as they are reported, whether spontaneously volunteered by a subject or in response to questioning about well-being at each study visit. The subject will be questioned in a general way and no specific symptoms will be suggested. The questioning about AEs will cover the current visit and the period of time between the previous and current visit although subjects may report AEs occurring at any other time during the study. Follow-up of all AEs will continue until the overall clinical outcome is definitive.

## 8.6. Evaluation of Adverse Events and Serious Adverse Events

### 8.6.1. Assessment of Intensity

The Investigator will assess the intensity for each AE and SAE reported during the study and will assign it to one of the following categories:

Mild	An event that is noticeable, but easily tolerated by the subject, causing minimal discomfort and not interfering with usual daily activities, compared to subject's baseline.
Moderate	An event that is sufficiently discomforting to interfere with usual daily activities, compared to subject's baseline.
Severe	An event that prevents usual daily activities, compared to subject's baseline.

### **8.6.2. Assessment of Causality**

When an AE or SAE occurs, the Investigator should assess the relationship between the IMP and the occurrence of the event. The Investigator should use clinical judgment to determine the relationship and assign it to one of the following categories:

Related	Any event that has a reasonable temporal relationship with the administration of study medication or follows a response pattern known to be related with the study IMP.
Unlikely to be related	Any event that does not have a reasonable temporal relationship with the administration of study medication and does not follow a response pattern known to be related to the study IMP.
Not related	Any event that started before administration of study medication and/or for which there is a clear alternative explanation.

The same criteria will be used to assign causality to study procedures.

### **8.7. Follow-up of Adverse Events / Serious Adverse Events**

After the initial AE or SAE report, the Investigator is required to proactively follow each subject at subsequent visits/contacts. All AEs and SAEs will be followed until resolution, until the condition stabilizes, until the event is otherwise explained, or until the subject is lost to follow-up. New or updated information will be recorded in the originally completed data collection tool.

The Investigator is responsible for ensuring that follow-up includes any supplemental investigations that may be indicated, including (but not limited to) additional laboratory tests, histopathology or consultation with other health care professionals. If a subject dies during participation in the study or during a recognized follow-up period, the Investigator should provide a copy of any post-mortem findings, including histopathology.

### **8.8. Reporting of Adverse Events and Serious Adverse Events**

Once the Investigator determines that an event meets the definition of a SAE, the SAE should be reported to the pharmacovigilance provider (PV) and Sponsor within 24 h, regardless of the time that may have elapsed since the time the event occurred and regardless of the causal relationship of IMP to the event. Any follow-up information on a previously reported SAE should also be reported to the PV and Sponsor later as needed. SAEs should be followed up until resolved or until the event is considered chronic and/or stable outcome.

The PV provider in this study is A+ Science. Contact details and instructions for SAE reporting to PV provider and Sponsor's Medical Monitor will be located in the ISF. The PV provider reports all authority reportable AEs to the CA.

## 8.9. Reporting of Pregnancy

Subjects who become pregnant during the treatment period must receive no further study treatment and the pregnancy must be reported using the same procedure as for SAE (Section 8.7). Subjects who become pregnant once treatment administration has been completed may remain in the study and the pregnancy must be reported using the same procedure as for SAE. A Pregnancy Notification Form must be completed. The outcome of the pregnancy should be followed up until term or premature termination. A Pregnancy Outcome Form, to assess the health of the mother and any infants, should be completed and reported following the same procedure as the Notification Form.

## 9. PREMATURE STUDY AND TREATMENT STOPPING CRITERIA FOR COHORTS 3 AND 4

The progress of the study will be monitored by the SRC (see Section 3.3.) The committee will review all safety data at timepoints defined in the study design (see Section 3) and will make recommendations regarding continuation, suspension or modification of dosing.

### 9.1. Study Stopping Criteria

The Sponsor reserves the right to prematurely terminate the study for valid scientific or administrative reasons.

For reasons of safety, further dosing in the study will be suspended and all safety data will be reviewed by the SRC if any of the following happens:

- Death of a study participant possibly attributable to study treatment or procedure.
- One Grade 4 systemic allergic reaction according to the WAO classification, following injection of the study IMP.
- Two Grade 3 systemic allergic reactions according to the WAO classification, following injection of the study IMP in 2 participants in the same cohort.
- One Grade 4 injection site reaction in 3 participants in the same cohort.

If a decision to suspend dosing in the study is reached, the SRC will review thoroughly all safety data and will determine whether:

- Dosing (scheduled or adjusted) may be re-started in current or subsequent cohorts.
- The study must be stopped and no additional subjects be dosed.

The EC and the CA will be informed, if the study is terminated prematurely. The Investigator will proceed to appropriate actions concerning the study subjects in the case of premature termination of the study.

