### **VISIT 2**

Subjects allocated into cohorts 3 and 4 (Table 8) will enter Turku University Hospital's Emergency Care unit, and after a brief medical review and other eligibility assessments they will receive a single s.c. injection of 30 ng of DM-101 or placebo. The subjects will remain confined in the hospital for approximately 6 h following dosing.

Dosing will be staggered in such a way that 2 sentinel subjects, 1 receiving DM-101 and 1 receiving placebo, will be dosed first in a double-blind fashion. Dosing of the remaining subjects in the cohort will be initiated no sooner than 22 h after the sentinel subjects have completed their Visit 2 dosing, without safety findings that would meet the study's stopping or treatment discontinuation criteria (see Section 9). Subjects in the main treatment group in each cohort will also receive treatment in a staggered way, with 2 subjects starting first to receive doses and the remaining subjects starting to receive doses no sooner than approximately 22 h after the first two subjects of the main group have received their Visit 2 dosing.

Visit 2 of cohort 4 subjects will take place after Visit 2 of cohort 3 has been completed.

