### **VISITS 3-6**

After Visit 2, dosing in each cohort will be allowed only if the study's stopping and treatment discontinuation criteria have not been met on the previous dosing visit (see Section 9).

All subjects will return to the hospital for another 4 visits (Visit 3, Visit 4, Visit 5 and Visit 6) on a biweekly basis for the subsequent dosings. In cohort 3, subjects will receive a single s.c. injection on each of these visits. In cohort 4, subjects will receive a single s.c. injection on Visits 3 and 4 and a series of 2 or 3 s.c. injections on Visits 5 and 6, respectively, with a minimum of 30 min interval between subsequent injections. Each injection will be given at a slightly different site of the exterior surface of the upper arm. The injections will alternate between the right and left arm.

Dose escalation to the 200 ng daily dose (Visit 5) in cohort 4 will only take place after a favourable recommendation from the SRC, once it has reviewed all available safety data so far collected in the study, including data from Visit 5 of cohort 3.

On each of the Visits 3-6, dosing will be staggered in the same way as on Visit 2, i.e. 2 sentinel subjects, 1 receiving DM-101 and 1 receiving placebo, will be dosed first in a double-blind fashion. Dosing of the remaining subjects in the cohort will be initiated no sooner than 22 h after the sentinel subjects have completed their dosing, without safety findings that would meet the study's stopping or treatment discontinuation criteria (see Section 9). Subjects in the main treatment group in each cohort will also receive treatment in a staggered way, with 2 subjects starting first to receive doses and the remaining subjects starting to receive doses no sooner than approximately 22 h after the first two subjects of the main group have received their dosing.

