### **Visits 3, 4, 5 and 6**

After Visit 2, all subjects will return to the hospital on a biweekly basis for the subsequent dosings, to receive either a single s.c. injection or a series of 2 or 3 s.c. injections of the study medication. All dosings, except the 4th and 5th dosings of cohort 4, involve only single injections. In cohort 4, the administration of the study medication at Visits 5 and 6 involves 2 and 3 s.c. injections, respectively. There will be a minimum of 30 min interval between subsequent injections. Each injection will be given at a slightly different site of the exterior surface of the upper arm. The injections will alternate between the right and left arm.

On each of the Visits 3-6 dosing will be staggered in the same way as on Visit 2, ie. 2 sentinel subjects, 1 receiving DM-101 and 1 receiving placebo, will be dosed first in a double-blind fashion. Dosing of the remaining subjects in the cohort will be initiated no sooner than 22 h after the sentinel subjects have completed their dosing, without safety findings that would meet the study's stopping or treatment discontinuation criteria (see Section 9).

Subjects in the main treatment group in each cohort will also receive treatment in a staggered way, with 2 subjects starting first to receive doses and the remaining subjects starting to receive doses no sooner than approximately 22 h after the first two subjects of the main group have received their dosing.

Visit 5 dosing of cohort 4 will only take place after a favorable recommendation from the SRC, once it has reviewed all available safety data so far collected in the study, including data from Visit 5 of cohort 3.

Dosing will only be allowed if the study's stopping and treatment discontinuation criteria have not been met.

Subjects will be contacted by telephone approximately 12 and 24 h after completion of dosing for a safety interview after each dosing visit.

Table 12 (for cohort 3) and Table 13 (for cohort 4) (see Section 6.5) show the procedures that will take place, before and after dosing, during the visits. All subjects will remain confined in Turku University Hospital's Emergency Unit for approximately 6 h following their dosing, and may then be discharged if the medical review by the Investigator or a designee is satisfactory.

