## 9.2. Treatment Stopping Criteria

For an individual subject, dosing of study IMP will be discontinued if any of the following happens:

- One Grade 4 systemic allergic reaction according to the WAO classification, following injection of the study IMP.
- Two or more Grade 3 systemic allergic reactions according to the WAO classification, following injection of the study IMP.
- One Grade 4 injection site reaction.
- Two Grade 3 injection site reactions following two injections.
- An AE or need for medication not consistent with the protocol requirements that, in the judgment of the Investigator, presents an unacceptable consequence or risk to the subject.
- Inability or unwillingness to comply with the study protocol or protocol deviation that is considered sufficient to jeopardize the subject's well-being or the integrity of the study.
- Pregnancy during study participation.
- Withdrawal of consent

Discontinuation of dosing will not necessarily result in withdrawal of the subject from the study. For the subjects who discontinue treatment, all safety assessments scheduled for the Follow-up will be requested and observations will be recorded.

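### Section 9.1 does not suspend dosing study-wide by rule after a related, non-fatal serious event that is neither a systemic allergic nor an injection site reaction

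*Protocol*

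**What the plan says.** Protocol Section 9.1 states that "further dosing in the study will be suspended and all safety data will be reviewed by the SRC if any of the following happens". Four events follow: a death possibly attributable to treatment or procedure; one Grade 4 systemic allergic reaction; Grade 3 systemic allergic reactions in 2 participants of the same cohort; and Grade 4 injection site reactions in 3 participants of the same cohort.

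For serious events in general, Section 8.8 says "the SAE should be reported to the pharmacovigilance provider (PV) and Sponsor within 24 h", and Section 8.3 says "In this FiH study, all adverse reactions to DM-101 will be considered unexpected". Both concern reporting.

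For the individual subject, Section 9.2 stops dosing after an adverse event that, "in the judgment of the Investigator, presents an unacceptable consequence or risk to the subject". The dosing gates draw on the same criteria; Section 6.3 (Visits 3 to 6) says "Dosing will only be allowed if the study's stopping and treatment discontinuation criteria have not been met".

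On cohort timing and committee review, Section 3.2 says "Visit 2 of cohort 4 subjects will take place after Visit 2 of cohort 3 has been completed" and "Dose escalation to the 200 ng daily dose (Visit 5) in cohort 4 will only take place after a favourable recommendation from the SRC". That review covers all safety data collected in the study so far. Section 3.3 also makes the SRC responsible for a recommendation on continuing cohort 3 to Visit 6, and allows further meetings as needed.

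**The concern.** Dosing on more than one day is new in humans in cohorts 3 and 4. Cohort 1 was a single dose, and no DM-101 subject in cohort 2 started Day 2 (Section 1.2.3). The two cohorts may be dosed in the same weeks. Section 12 accepts that adverse events by an unexpected, non-allergic mechanism are always possible at this stage, while calling their likelihood small, and says the allergy precautions apply to them too. For the automatic hold in Section 9.1 that is true only of a fatal event. After a related, non-fatal serious event of another kind, other subjects could reach their next scheduled dose before any committee has looked at the data, unless someone decides to stop.

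**Working it through.** The plan gives no operating characteristic to reproduce, so the check is mainly of rules against rules.

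**1. Triggers.** Of the four events in Section 9.1, 0 cover a related, non-fatal serious event outside the two reaction categories. The SAP contains no stopping rule.

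**2. Other routes to a hold.**

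| Route | Where | Set off by | Reach |
|---|---|---|---|
| Expedited reporting | 8.3, 8.8 | Serious event | No dosing hold attached |
| General adverse event criterion | 9.2 | Investigator's judgment | That subject |
| Sentinel gate | 3.2, 6.3 | A 9.1 or 9.2 criterion met | Rest of the same cohort |
| Between-visit gate | 3.2 | As above, at the previous dosing visit | Each cohort |
| General dosing conditions | 1.2.3, 6.3 | As above, or safety in general | No cohort named in 6.3 |
| Discussion with Medical Monitor before dosing | 5.1.6.2 | A finding of concern | The dosing in hand |
| Ad hoc SRC meeting | 3.3 | As needed, or a Section 9 observation | Whole study |
| Scheduled SRC reviews | 3.2, 3.3, 6.3 | Fixed timepoints | Cohort 4 Visit 5 (all study data); cohort 3 Visit 6 |
| PI and SRC review before later cohorts | 12 | Progression | Start of cohort 4 |
| Sponsor's right to terminate | 9.1 | Sponsor's decision | Whole study |

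No route holds dosing by rule because such an event has occurred. The gates need the 9.2 criterion to be met, and for this kind of event that is a judgment. The Section 6.3 condition names no cohort, but 9.2 also lists withdrawal of consent. Read as study-wide, it would stop everyone when one subject withdraws, so it reads more naturally as a condition on the subject.

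**3. Time between scheduled reviews.** Cohorts 3 and 4 have 2 × 4 = 8 return dosing visits (Visits 3 to 6). Section 3.3 places a scheduled SRC recommendation before two: cohort 4 Visit 5 and cohort 3 Visit 6. That leaves 8 − 2 = 6: cohort 3 Visits 3, 4 and 5, and cohort 4 Visits 3, 4 and 6. The synopsis puts escalation in general under SRC review. Sections 1.2.3, 3.2, 3.3 and 6.3 turn this into one review before doses above 100 ng, which is the reading used here.

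**4. Experience so far (Section 1.2.3, Tables 6 to 8).**
- Treatment-emergent events: 16 + 58 = 74, of which 0 + 0 = 0 serious.
- Placebo events: 3 + 2 = 5, of which 0 recorded as IMP-related.
- DM-101 subjects: 4 + 4 = 8, none with a serious event. Exact 95% upper bound: 1 − 0.05^(1/8) = 0.312 one-sided; 1 − 0.025^(1/8) = 0.369 two-sided.
- Highest single injection given in cohort 2 against the new daily maximum: 5,000 / 300 = 16.7.

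**5. How often an added trigger would fire.** The documents give no risk p per subject, so p is an assumption. The chance of at least one trigger is 1 − (1 − p)^n, with n = 16 if placebo subjects carry the same p (causality is assessed blinded) and n = 12 if only DM-101 subjects do.

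| Assumed p | n = 16 | n = 12 |
|---|---|---|
| 0.5% | 7.7% | 5.8% |
| 1% | 14.9% | 11.4% |
| 2% | 27.6% | 21.5% |
| 5% | 56.0% | 46.0% |

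Under the present Section 9.1, the chance that such an event suspends dosing automatically is 0 at any p.

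**The case against.** A reader might infer that nothing could stop dosing in the other cohort after such an event. The documents do not support that. The review before cohort 4 Visit 5 covers the whole study, the SRC also decides on cohort 3 Visit 6, and it can meet at any time. This is one site with all dosing in one unit, the Principal Investigator and Medical Monitor sit on the SRC, serious events reach the Sponsor within 24 h, and each subject's doses are two weeks apart. The people who would order a hold would know of the event. In March 2020 the SRC advised against further dosing with no criterion met. That shows judgment can work, although dosing had already stopped three days earlier because of the pandemic.

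It can also be said that the added bullet moves judgment rather than removing it, since for causality "The Investigator should use clinical judgment to determine the relationship and assign it to one of the following categories". This stands in part. What changes is that, once causality is assigned, the hold follows by rule and covers both cohorts.

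The likelihood argument is fair too. Section 12 names allergic reaction as the main risk. Rabbits given up to 500 µg every two weeks over 10 weeks showed no significant effects, and cohort 2 went well above the new doses. The bullet would also be stricter for a less likely risk: one related non-allergic serious event would pause the study, while one serious Grade 3 systemic reaction would not. That asymmetry is defensible, because allergic reactions are anticipated and have a grading scale and a treatment algorithm, whereas an unexpected mechanism has neither.

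**Conclusion.** The point holds in a narrow form. Several controls reduce the risk, but between the scheduled reviews a hold after this kind of event rests on judgment, while the listed allergic and injection site reactions stop dosing by rule. It is a low-cost safety improvement, and no event rate is claimed.

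A reader might take the 31% or 37% bound as evidence of a high risk. It is not. It is what 0 of 8 gives in any setting, it covers all serious events, and it comes from one-day dosing. It shows only that the data so far cannot exclude the risk.

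Two limits apply. The separate SRC Instructions (Section 3.3) were not available and may contain such a trigger. The SAP (Sections 2, 17 and 20) works from protocol version 3.1, while the protocol text reviewed describes version 2.0, so the current Section 9.1 may differ.

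**What to change.** First check Section 9.1 of the current protocol version and the SRC Instructions. If the trigger is absent from 9.1, add one bullet: *Any serious adverse event assessed as related to the IMP in any participant, other than a systemic allergic reaction or injection site reaction (which are governed by the graded criteria above).* The existing lead-in, SRC and 24 h reporting then pause dosing until the data are reviewed.

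The exception is needed. Section 8.4.1 allows overnight hospitalisation after a Grade 3 systemic reaction, which makes it serious under Section 8.2. Without the exception, one such reaction would override the two-participant rule.

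Costs: a substantial amendment with ethics committee and authority approval (Section 11.4) and, if triggered, an extra SRC meeting and a pause. A pause beyond the visit windows of 1 to 2 days causes deviations. Close to the birch pollen season it could cost remaining doses, since Sections 1.4 and 12 place treatment outside the season, and SAP Section 2 gives the coming season as one reason for not restarting in 2020. The definition of related in Section 8.6.2 is broad, so an event in a placebo subject could trigger the pause. Prompt SRC review, unblinded if needed as Section 3.3 allows, should keep it short.
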